#### **14) Withdrawal of Subjects\***

Subjects will be withdrawn from the study if they are determined to meet ineligibility criteria after enrollment. If subjects have laboratory results that meet the exclusionary criteria range during the study, the subject will have his/her labs repeated before being withdrawn from the study.

The study medication will be stopped if a subject has a serious adverse event, but will not necessarily be stopped for exacerbation of psychiatric symptoms or any other adverse event. If the PI or co-investigator considers continuation of the study medication to be safe after a worsening of psychiatric symptoms, and the subject wishes to continue, the subject's treating psychiatrist will be contacted and will make the final decision whether the subject will be allowed to continue taking study medication.

Female subjects may be terminated from the study if they become pregnant at any time while participating in the study. Subjects who fail the urine screening for illegal drugs during the screening visit will be deemed a screen fail and terminated from the study. We will not document the results from the urine drug screen in the patient study records. We will maintain a separate log of the reasons for screen fail. This log will have the counts of screen fails for various exclusion factors including current substance abuse. This log will have no subject information and will have no link to subject id.

Subjects may also withdraw their consent from the study at any time for any reason, including: physical or emotional discomfort associated with taking the study medication, physical or emotional discomfort associated with performing study procedures, or inability to come in for required study visits.

If at any time the study sponsor or research personnel at UMass decide to terminate the study, subjects' consent will be withdrawn involuntarily.

For subjects terminated or withdrawn from the study, they will be asked to have an "exit" visit. Vital signs, ECG, side effect assessment and routine blood tests (CBC, basic metabolic profile) will be performed during the visit.

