### **Exclusion Criteria:**

- 1) inability to provide informed consent, or for individuals with a legal guardian, inability to provide assent or a lack of informed consent from the legal guardian
- 2) current substance abuse
- 3) Subjects who are not on a stable dose of an antipsychotic medication for at least a month prior to enrollment
- 4) psychiatrically unstable per treating clinician's judgment
- 5) Uncontrolled medical condition including uncontrolled hypertension, diabetes, seizure disorder, severe cardiovascular, cerebrovascular, pulmonary, thyroid diseases, and gastroparesis.
- 6) history of ketoacidosis
- 7) currently taking insulin
- 8) currently taking meglitinides (repaglinide and nateglinide)

- 9) currently on immunosuppressant medication regularly including oral steroids; topical and inhalant steroids are allowed
- 10) currently on sulfonylurea drugs (e.g. glyburide)
- 11) Current, active chronic infection (including tuberculosis, HIV and hepatitis), malignancy, organ transplantation, blood dyscrasia, central nervous system demyelinating disorder, and any other known autoimmune or inflammatory condition
- 12) pregnant or breastfeeding.
- 13) prisoners
- 14) Exclusionary labs: eGFR < 35 ml/min

Hematology (CBC)	
Leukocytes	<2 or $>17.5 \times 10^3/\text{mm}^3$
Platelets	<75 or $>700 \times 10^3/\text{mm}^3$
Comprehensive Metabolic Panel	
Sodium	<1.1 times the lower limit ( $\leq 121.5$ ) or $>1.1$ times upper limit ( $\geq 159.5$ ) of the reference range
Potassium	<1.1 times the lower limit ( $\leq 3.15$ ) or $>1.1$ times upper limit ( $\geq 5.83$ ) of the reference range
Glucose	$>2$ times the upper limit ( $>198$ ) of the reference range
Blood Urea Nitrogen (BUN)	$>1.3$ times upper limit ( $>29.9$ ) of the reference range
Creatinine	$>1.3$ times upper limit ( $>1.69$ ) of the reference range
Total bilirubin	$>2$ times the upper limit ( $>2.4$ ) of the reference range
Aspartate amino transferase (AST)	$>3$ times upper limit ( $>120$ ) of the reference range
Alanine amino transferase (ALT)	$>3$ times upper limit ( $>120$ ) of the reference range
Alkaline phosphatase (ALP)	$>3$ times upper limit ( $>345$ ) of the reference range
Hemoglobin A1C	Patients with a value $\geq 9.0\%$

All exclusionary labs will be reviewed prior to administration of the study drug.

We will continue our recruitment efforts to assure a meaningful representation of women and minority populations.

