## **12) Data Management\***

All data management will be conducted in the research offices of the Biotech One building. Standard data forms for the clinical rating scales will be used for this project. Individual notebooks will be maintained for each subject that will include signed consent, letter to halfway house, subject information sheets, raw data from clinical rating scales, laboratory measurements and a study timetable or flow sheet for that subject. A study database will be created using the REDCap system. The data will be stored on a secure server in the UMass HIPAA-compliant data center with daily backup. The database will be designed by the PI and maintained by the PI and the research staff. Data entry will be performed by research coordinators and will be reviewed by the research manager and the PI for accuracy. Access to the database will be restricted by password. All data will be stored safely for 5 years.

There are no published data yet about exenatide's effects on clinical symptoms and cognition in the schizophrenia population. This study is intended as an initial test of efficacy. Repeated measures of clinical symptoms and cognitive performance will be analyzed in separate linear mixed models with fixed effects of visit, treatment group, baseline score, and visit x treatment and visit x baseline score interactions and random participant-specific intercepts and slopes. Potential confounding variables will be included as covariates. The effect of exenatide on 24-week change from baseline will be determined by the estimated regression coefficient of the visit x group interaction term. The sample of 60 evaluable subjects will have 80% power to detect an effect size of 0.74 based on a two-tailed t-test at alpha = 0.05.

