Continuous data and safety monitoring will be conducted by the PI. The monitoring will include all adverse events (AEs and SAEs) both expected and unexpected, enrollment, dropout rates and protocol deviations in addition to the results of special studies and laboratory tests that are conducted to ensure patient safety, subject interview and conduct, review of subject symptom or performance status, review of clinical test results, review of subject physical examination, review of all vital signs, diagnostic tests, and evaluations. The investigator will report adverse events to the IRB in accordance with IRB guidelines.

The PI will create a Data Safety Monitoring Board (DSMB) to independently oversee this clinical trial. The DSMB for this study will be composed of at least three people and will include a psychiatrist, an endocrinologist and a biostatistician who will be independent of the study group. The group will follow the NIH policy for data and safety monitoring and guidelines as published on <http://www.nimh.nih.gov/research-funding/grants/nimh-policy-on-data-and-safety-monitoring-in-extramural-investigator-initiated-clinical-trials.shtml>. Study data regarding subject enrollment, characteristics, symptoms, adverse events and serious adverse events will be submitted to the DSMB for review and analysis annually. The DSMB will review study data, the safety of study participants and conduct of the study. It will advise the PI on continuation of the study and provide reports to the IRB regarding recruitment of appropriate subjects and presence of adverse effects.

An explicit stopping rule will be followed for a potentially serious psychiatric decompensation in order to further enhance patient safety: active subjects will be terminated from the study if they experience an increase in PANSS total score greater than or equal to 20 compared to their baseline score at any point during the study.

Subjects will be terminated from the study if their eGFR falls below 30 ml/min at any point during the study.

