Statistical analysis: Statistical analysis was performed using SPSS (version 24.0, IBM Corp, Armonk, NY, USA). Descriptive statistics were performed to summarize demographic and clinical characteristics of the study sample. Group comparisons were performed using independent samples t test for continuous variables and the Fisher exact test or Chi-square test for categorical variables. The outcome measures were repeated at different time points. Therefore, analysis of repeated measures using mixed models was performed to compare the change over time in outcome measures between the two treatment groups while controlling for potential confounding variables. The mixed model approach does not require subjects to have the same number of study visits or measurements and uses all available data instead of eliminating subjects with missing data, resulting in unbiased estimates of the model parameters when data are missing at random. Further, for those who completed 24-week treatment, analysis of covariance (ANCOVA) was used to compare change scores from baseline to week 24 between the two treatment groups controlling for potential confounding variables. For all analyses, a P value less than 0.05 (two-tailed) was used for statistical significance.

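### Safety and laboratory rules end outcome follow-up as well as study participation, so week 24 ratings are lost for reasons treatment may influence

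*Protocol*

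**What the plan says.** **Rules that end participation**

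- Protocol Section 13, psychiatric rule: "active subjects will be terminated from the study if they experience an increase in PANSS total score greater than or equal to 20" points above baseline.
- Protocol Section 13, renal rule: "Subjects will be terminated from the study if their eGFR falls below 30 ml/min at any point during the study".
- Protocol Section 14, laboratory values in the exclusionary range during the study: "the subject will have his/her labs repeated before being withdrawn from the study". Through the Section 5 table that range includes glucose above 198, HbA1c of 9.0% or more and creatinine above 1.69, and Section 5 also lists "Exclusionary labs: eGFR < 35 ml/min".
- Protocol Section 14, general rule: "Subjects will be withdrawn from the study if they are determined to meet ineligibility criteria after enrollment".

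**What follows removal.** Section 14 describes one exit visit with vital signs, ECG, side effects and routine bloods. It lists no SANS, MCCB or PANSS, and neither document provides for rating removed subjects at later visits. Section 14 uses different words for a serious adverse event, where it is the medication that stops. Leaving the study and leaving the drug are therefore worded as separate things.

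**Ratings and analysis.** SANS, PANSS and MCCB belong to one assessment, done at baseline and at weeks 6, 12, 18 and 24 (Protocol Section 10). The SAP fits a mixed model to all available data, "resulting in unbiased estimates of the model parameters when data are missing at random", and adds an ANCOVA of change to week 24 restricted to subjects who completed treatment. It names no sensitivity analysis for departures from missing at random, and does not say whether a randomised subject later found ineligible is analysed.

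**The concern.** The triggers are measured after randomisation, and treatment may move them. PANSS total, glucose and HbA1c are trial outcomes in Protocol Section 3, and altered renal function is a listed risk in Section 15. When such a trigger ends outcome follow-up, the week 24 value is missing for a reason that may be related to treatment, and the balance of removals may differ by arm.

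Two things are at stake. First, the comparison of all randomised subjects at week 24 is no longer observed. The mixed model fills the gap by assuming that removed subjects would have followed the course of those who stayed, given their recorded data. Second, the completers-only ANCOVA compares the arms among those who survived these rules, and that group is not protected by randomisation. Ratings that were never taken cannot be recovered in analysis.

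**Working it through.** **1. The plan's own figure.** Inputs from Protocol Section 12: 60 evaluable subjects (30 per arm at 1:1), standardised effect 0.74, two-sided alpha 0.05.

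- Noncentrality = 0.74 × √(30/2) = 2.87, with 58 degrees of freedom. Power is 80.5%, so the stated 80% is reproduced.
- Implied allowance for loss: 70 − 60 = 10 subjects, or 10/70 = 14.3%. No dropout rate is stated.

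**2. Ratings lost.** Four post-baseline ratings are scheduled.

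| Removed at | Ratings lost | Number |
|---|---|---|
| Week 6 | 12, 18, 24 | 3 of 4 |
| Week 12 | 18, 24 | 2 of 4 |
| Week 18 | 24 | 1 of 4 |

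Week 24 is lost in every row.

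**3. Likely direction of each trigger**

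| Trigger | Link to treatment | Arm that may lose more |
|---|---|---|
| PANSS rise of 20 or more | exploratory outcome | placebo, if the drug lowers PANSS |
| Glucose, HbA1c | exploratory outcomes | placebo, if glycaemia improves |
| eGFR, creatinine | listed risk | exenatide, if renal function falls |

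The net direction is not determined.

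**4. How many the PANSS rule might remove.** The documents give no SD for PANSS change. Assume SD 8, 10 or 12, lag-1 correlation 0.7 and no true change. The chance of reaching +20 at week 6, 12 or 18 is then 1.5%, 5.2% or 10.3%. Multiplied by 70, that is about 1, 4 or 7 subjects. Seven removals leave 63, with power 82% at 0.74. The documents offer no basis for counting laboratory removals.

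**5. Possible bias in SANS (illustrative).** Assumed: PANSS change SD 10 to 15, SANS–PANSS correlation 0.3 to 0.6, within-subject correlation 0.6, course unaffected by removal, and PANSS lowered by 0.74 SD on exenatide.

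- Removed: 5% to 19% on placebo, 2% to 10% on exenatide.
- Completer comparison with a true SANS effect of 0.74 SD: attenuated by about 0.01 to 0.05 SD.
- Completer comparison with no true SANS effect: biased by about 0.01 to 0.05 SD against the drug.
- Likelihood analysis of all observed SANS data: bias within about 0.001 SD. This model satisfies missing at random by construction, so the result does not test that assumption.

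**6. What continued follow-up does to power.** Suppose all 70 are rated, and 5 of 35 exenatide subjects are off drug and keep a fraction k of the effect. Then d = 0.74 × (30 + 5k)/35.

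| k | d | Power, 35 per arm |
|---|---|---|
| 1 | 0.740 | 86.3% |
| 0.5 | 0.687 | 80.9% |
| 0 | 0.634 | 74.4% |

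The gain is less selective missingness, not assured power.

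**The case against.** The case for leaving the plan alone has real strength.

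- **The general ineligibility sentence is weak evidence.** The protocol enrols 110 to randomise 70, so enrolment comes before randomisation. The sentence naturally covers screening failures, who have no ratings to lose, and ineligibility present at entry is not caused by the drug. This stands. The point needs only the on-study laboratory rule and the two Section 13 rules.
- **The rating at the trigger visit is usually recorded.** SANS and PANSS are done together, and the mixed model uses partial data. Removals on PANSS may therefore be close to missing at random given observed SANS. This stands for the mixed model. It does not help the ANCOVA, and neither PANSS nor the laboratory triggers are named in the SANS model.
- **The SAP's claim is conditional and correct as worded.** This stands. What is missing is any check on the condition.

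A reader might go further and infer that the mixed model is shown to be biased. With other assumptions (10–15% of placebo and 3–5% of exenatide subjects decompensating, SANS worsening with a lag), simulated likelihood-based week 24 differences move from −5.48 to −5.27, −5.91 to −5.53 and −1.04 to −0.60 points. The last looks like a loss of about 40%, but it is 0.44 points on a small effect. If 5.5 to 6 points is taken as 0.74 SD, 0.44 points is about 0.06 SD, against a standard error of √(2/30) = 0.26 SD. None of these inputs is in the documents.

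A reader might also infer that power falls below plan, for example to 74% with 52 evaluable subjects. That needs 70 − 52 = 18 losses, for which the documents give no basis.

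**Conclusion.** The point holds on the text. The PANSS, eGFR and on-study laboratory rules end the study for the subject, and no SANS or MCCB rating is provided for afterwards. A randomised subject removed at week 6, 12 or 18 loses 3, 2 or 1 of four post-baseline ratings, always including week 24, on triggers that treatment may change.

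The consequence is bounded. The mixed model is unbiased only under missing at random, which is neither shown to hold nor shown to fail. The completers-only ANCOVA is the most exposed analysis. The illustrative bias there is 0.01 to 0.05 SD, and the documents settle neither its size nor its direction. The documents do not support reading Section 12 ("The sample of 60 evaluable subjects will have 80% power to detect an effect size of 0.74") as failing: that figure reproduces, and assumed chance crossings of the PANSS rule stay within the implied allowance of 10.

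This is a worthwhile, inexpensive improvement rather than a defect that invalidates the trial.

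**What to change.** 1. Leave every clinical trigger and the decision on study drug as the protocol team sets them. In Sections 13 and 14, separate them from outcome follow-up: whatever the drug decision, randomised subjects who have not withdrawn consent are invited to the remaining scheduled SANS and MCCB visits.
2. In the SAP, state that all randomised subjects, including any found ineligible later, are analysed in their allocated arm, and label the completers-only ANCOVA supportive.
3. Separately, reconcile two pairs of statements; this review does not say which is right. Section 13 makes termination mandatory at a PANSS rise of 20, while Section 14 allows medication to continue after psychiatric worsening. Section 13 terminates at an eGFR below 30, while Section 14 reapplies the exclusionary laboratory range, which Section 5 sets at an eGFR below 35.

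**Cost.** Protocol and consent wording, plus up to three existing rating visits for a few subjects. The full week 24 visit takes about 5 hours, and some subjects will decline. The SAP, dated 11/30/2019, describes visits in the past tense. If follow-up is already complete, only item 2 can still change the analysis.

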## **22) Resources Available**

All research personnel have completed CITI training and are aware of Good Clinical Practices (GCP). The PI is a senior psychiatrist who specializes in schizophrenia treatment and research. Both the Principal Investigator and Co-Investigator each have more than 10 years of experience working with individuals suffering from schizophrenia and substance abuse.

The study coordinator (i.e. research assistant) will be involved in activities such as reviewing study procedures with each subject, obtaining informed consent, data-entry, and blood sample collection. The study coordinator will also be responsible for administering questionnaires and conducting assessments. The study coordinator is certified in phlebotomy, and has completed sufficient training in order to obtain informed consent, conduct study assessments, enter data, etc.

The PI will be held responsible for oversight of the study procedure. The PI and Co-Investigator will also be responsible for identifying AEs and SAEs and for terminating a subject if their physical and/or mental health is compromised as a result of the study treatment.

Research nurses who are qualified registered nurses (RN) may be involved in study activities such as administering Exenatide injections and completing questionnaires and other study assessments.

The PI will discuss individual roles with each member of the research team once the study commences.

The PI can be contacted by phone and the UMass Memorial Emergency Service is available for psychiatric and medical assessment of research subjects.

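### Protocol section 14 makes termination for pregnancy optional although pregnancy is excluded elsewhere; no text explicitly stops injections, and no pregnancy test is scheduled after screening

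*Protocol*

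**What the plan says.** Two sentences in Protocol section 14 can apply to a pregnancy that begins after enrollment.

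- The opening sentence is mandatory: "Subjects will be withdrawn from the study if they are determined to meet ineligibility criteria after enrollment". Item 12 of the exclusion criteria in section 5 is "pregnant or breastfeeding", and section 17 (Vulnerable Populations) also rules pregnant women out of participation.
- The later sentence, the only one in the section about pregnancy, is permissive: "Female subjects may be terminated from the study if they become pregnant at any time while participating in the study".

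On study drug, section 14 has one mandatory stop: "The study medication will be stopped if a subject has a serious adverse event". Pregnancy is not mentioned there.

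On detection, section 10 puts a urine pregnancy test at the screening visit for women of childbearing potential. Section 13 describes the same testing as part of enrollment. Inclusion criterion 6 requires birth control for these women, and section 10 adds weekly reminders.

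**The concern.** Pregnancy is a reason not to start the drug, so the plan should say plainly what happens when it arises during dosing. The sentence written for that case leaves the outcome to discretion and does not mention the injections. Under the mandatory rule a pregnant participant leaves the study and dosing ends. Under the permissive sentence she could stay, and no other text tells the site to withhold the next weekly dose.

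The testing schedule adds to this. With one test before the first dose and none afterwards, no scheduled test would reveal a pregnancy during the 24 weeks. At stake are participant safety and consistent conduct at the site. The analysis is not at stake.

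**Working it through.** The plan gives no figure to reproduce. The check compares the wording, then counts doses and tests.

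**1. Which sentence governs?**

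- *Pointing to mandatory withdrawal:* the opening sentence of section 14; exclusion 12; section 17; and the sentence that directly follows the opening one. That sentence deals with laboratory values that enter the exclusionary range while the subject is on study, and it provides for a repeat test before withdrawal. So the rule reaches criteria first met after entry, at least for laboratory values.
- *Pointing to an entry-only reading:* eGFR has an entry limit, "Exclusionary labs: eGFR < 35 ml/min", and section 13 sets a different on-study limit: "Subjects will be terminated from the study if their eGFR falls below 30 ml/min at any point during the study". If every exclusion carried over automatically, a second, lower limit would not be needed.
- *Result:* mandatory withdrawal is the more natural reading, but the pregnancy sentence contradicts it and no text says which takes precedence.

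**2. Does any text stop the injections?**

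- Section 14: only for a serious adverse event. For other adverse events the drug is not necessarily stopped.
- Section 13: termination for a PANSS total increase of 20 or more, or for eGFR below 30. Pregnancy is not listed.
- Section 22: the investigators are responsible "for terminating a subject if their physical and/or mental health is compromised as a result of the study treatment". This concerns harm from treatment and does not name pregnancy.
- Section 32 (Drugs or Devices): nothing on pregnancy.
- *Result:* withdrawal or termination ends dosing by implication. No rule covers a pregnant participant who is not terminated.

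**3. Where is a pregnancy test listed?**

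- Screening: yes.
- Baseline, weeks 1-23 and week 24 (section 10, and the SAP's visit descriptions): none.
- Exit visit (section 14): none. "Vital signs, ECG, side effect assessment and routine blood tests (CBC, basic metabolic profile) will be performed during the visit".

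**4. Injections per test**

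- Injections: baseline (1) + weeks 1-23 (23) = 24, in line with 24 weeks of weekly dosing in section 32.
- Now: 24 injections follow the single test.
- With a test before the injection at baseline and weeks 6, 12 and 18, the runs are weeks 0-5, 6-11, 12-17 and 18-23, which is 24 / 4 = 6 each.
- The SAP describes injection visits as weeks 1-24. Taken literally, that gives 1 + 24 = 25 injections. The last run (weeks 18-24) would then be 7, or 6 if a week 24 test came before that injection.

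**5. Number of tests**

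The documents do not give the number of women of childbearing potential. Assuming 10 to 35 of the 70 randomised:

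- 4 tests each: 4 × 10 = 40 to 4 × 35 = 140.
- 5 tests each, with week 24: 5 × 10 = 50 to 5 × 35 = 175.

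**6. Outcome data if she is withdrawn rather than taken off drug**

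SANS and MCCB are due at weeks 6, 12, 18 and 24, which is 4 post-baseline assessments. The exit visit includes neither. If each visit's assessment is completed before withdrawal:

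| Pregnancy found | Assessments lost if withdrawn | Lost if followed off drug |
|---|---|---|
| Before week 6 | 4 | 0 |
| Week 6 | 3 | 0 |
| Week 12 | 2 | 0 |
| Week 18 | 1 | 0 |

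**The case against.** The best reply is that the protocol is clear enough when read as a whole. Exclusion 12, section 17 and the opening of section 14 all point to exclusion, and a single *may* should not be read as overriding them. This largely stands. A reader might infer that the protocol intends to keep dosing pregnant women. The documents do not support that: the weight of the text is for withdrawal, and withdrawal ends the injections. What remains is that the sentence a site would consult for pregnancy says something weaker than the rest.

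A reader might also infer that a pregnancy would go unnoticed. That goes too far. Birth control is required, reminders are weekly, and section 13 has participants meet a study psychiatrist at each visit. Section 20 foresees pregnancy during the study and refers to the results of such tests, which may imply testing after screening. It schedules none, however, and these safeguards reduce or may detect pregnancy without replacing a planned test.

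Two further limits stand. Consent pages were removed before review and may contain a stop rule or more tests. And section 15 lists no fetal or reproductive risk and no pregnancy rate is given, so the harm avoided cannot be sized; the number and timing of tests is a matter of judgement.

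**Conclusion.** The point holds as a low-cost safety clarification. Section 14 contradicts itself and sections 5 and 17 on pregnancy. Mandatory withdrawal is the likelier intent, but it is not what the pregnancy sentence says. No text explicitly stops injections for pregnancy, and no test is scheduled after screening.

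The size that can be stated is the dosing interval: up to 24 injections after one test, reduced to at most 6 on the Protocol's dosing schedule. A pregnancy that begins after the week 18 test could still be exposed up to week 23, because no later scheduled test comes before a dose.

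The documents support no claim about the amount of fetal harm or the number of pregnancies. The power statement (60 evaluable subjects, effect size 0.74) and the main mixed-model analysis are unaffected. The conclusion rests on the protocol and SAP text supplied, without the consent form.

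**What to change.** 1. In section 14, replace the pregnancy sentence with: *If a participant becomes pregnant once she is in the study, study medication is stopped immediately and the exit-visit safety checks (vital signs, ECG, side effects, routine bloods) are done. If she agrees, she may continue the planned clinical symptoms assessments off drug. For pregnancy, this rule takes precedence over the opening sentence of this section.*
2. In section 17, say that pregnant women may not be enrolled and may not receive study medication. Without this change, off-drug follow-up would contradict that section.
3. In section 10, add a urine pregnancy test for women of childbearing potential before the injection at baseline and at weeks 6, 12 and 18. At baseline it is best done before randomisation, so that a positive result is a screening failure. A week 24 test is optional: on the Protocol's schedule it can only detect exposure after the last dose.

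**Cost:** two amended passages, one added line at four existing visits, matching consent text, and 4 urine tests per woman of childbearing potential (5 with week 24). No new visits are needed. Off-drug scores can enter the mixed model, which uses all available data. She would not be in the SAP's ANCOVA, which is limited to those who completed 24 weeks of treatment. Because the SAP is written in the past tense, the change helps only participants still being dosed or a successor protocol.
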